5.2.2 Secondary Endpoints

The secondary endpoints will include:

- Incidence of Surgical Site Occurrence (SSO) which are the following Adverse Events (AEs) related to the study device, mesh, and / or study procedure and defined as Seroma, Hematoma, Surgical Site Infection (SSI), bleeding at tack implantation site following the MaxTack[™] Motorized Fixation Device used for fixation in minimally invasive ventral hernia repair procedures at the following timepoints:
 - by Discharge
 - o within 1 month
 - within 3 months
 - within 12 months
- Incidence of SSO requiring Procedural Intervention (SSOPI), which are the following AEs related to the study device, mesh, and/or study procedure and defined as Seroma, Hematoma, Surgical Site Infection, bleeding at tack implantation site following the MaxTack[™] Motorized Fixation Device used for fixation in minimally invasive ventral hernia repair procedures at the following timepoints:
 - by Discharge
 - o within 1 month
 - o within 3 months
 - o within 12 months
- Incidence of hernia recurrence following the MaxTack[™] Motorized Fixation Device used for fixation in minimally invasive ventral hernia repair procedures. The evaluation of hernia recurrence will be performed via a Valsalva maneuver during a physical examination and confirmed per site standard of care medical imaging, if necessary, at the following timepoints:
 - \circ within 1 month
 - o within 12 months
- Incidence of hernia recurrences resulting in reoperation, defined as an operative procedure performed with the specific goal of repairing the recurrent hernia, at the following timepoints:

- o within 1 month
- \circ within 3 months
- within 12 months
- Incidence of MaxTack[™] Motorized Fixation Device deficiencies (e.g., insufficient tack penetration, loose tacks, tack(s) migration, tacker issue battery etc.) on day of the index procedure.
- Operative time for mesh fixation, defined as the time elapsed from the initiation of the mesh fixation process with MaxTack[™] to its completion
 - Surgeon satisfaction as assessed by Surgeon Satisfaction Questionnaire postoperatively.
 - Length of hospital stay after minimally invasive ventral hernia repair procedure where the MaxTack[™] Motorized Fixation Device was used for fixation.
- Change in subject-reported pain at the hernia site evaluated with Numeric Rating Scale (NRS) score from 0 to 10 at screening and compared to the following timepoints:
 - o at Month 1
 - o at Month 3
 - o at Month 12

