12.1 Adverse Events

The following AEs are required to be reported in the study after the point of skin incision until the subject exists:

- All AEs related to the MaxTack[™] Motorized Fixation Device, mesh, or study procedure
- All events that lead to death, regardless of relatedness
- Any non-subject adverse event

Reporting of these events to Medtronic will occur on the applicable AE eCRF. Each event must be reported separately. Documented pre-existing conditions are not considered AEs unless the nature or severity of the condition has worsened. Subject deaths are required to be reported. Refer to Section 12.7 for Subject Death collection and reporting requirements.

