Serious Adverse Device Effect (SADE) (ISO14155:2020, 3.44)	Adverse device ef characteristic of a		has resulted in any of adverse event.	the consequences	
Device Deficiency (DD) (ISO14155:2020, 3.19)	durability, reliabili NOTE 1: Device de inadequacy in the labeling. NOTE 2: This defir	ity, usabi eficiencie informa nition inc	evice with respect to it ility, safety, or perform is include malfunctions tion supplied by the m ludes device deficienci vice or the comparator	ance. s, use errors, and anufacturer including es related to the	
Serious Health Threat (SHT) (ISO14155:2020, 3.46)	imminent risk of d users or other per subjects, users or NOTE 1: This woul nature such that t	leath or a sons, an other pe ld include hey becc	d that requires prompt rsons. e events that are of sig	in the health in subjects, remedial action for other nificant and unexpected ential serious health hazard	
Relatedness					
investigators will use th	Each AE will be classified according to four different levels of causality. The sponsor and the investigators will use the following definitions to assess the relationship of the AE to the MaxTack™ motorized fixation device, mesh, or study procedure. For purposes of analysis categories considered "related" will include Possible, Probable and Causal.				
Not Related	or proced the event (if the respination implausib the discor level of activation creintroduc activation the event affected b the event concurrent	has no t ure does no ponse pa le ntinuatio ctivation, ction of i /exposu involves oy the de can be a at illness,	emporal relationship w t follow a known respo attern is previously kno n of device application dexposure - when clinic ts use (or increase of the re), do not impact on the a body-site or an orga vice or procedure ttributed to another ca	or the reduction of the cally feasible – and he level of he event	

AFFIX (MaxTac Clinical Investi				
MDT23014	Revision	3.0	Page 52 of 97	Medtronic

	 the event does not depend on a false result given by the device used for diagnosis, when applicable In order to establish the non-relatedness, not all the criteria listed above might be met at the same time, depending on the type of device/procedures and the event. The relationship is weak but cannot be ruled out completely. Alternative 					

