12.3.1 Reporting Requirements and Timelines for Adverse Events and Device Deficiencies

All AEs and DDs need to be reported in a timely manner to the sponsor and to the IRB/EC per the IRB/EC reporting requirements. It is the responsibility of the investigator and the sponsor to abide by the AE and DD reporting requirements as stipulated by local law and the study site's IRB/EC.

Туре:	Report to:	Reporting Timeframe (from time of learning of event):
DD	Sponsor	Recommended within 10 working days
	IRB/EC	Per IRB/EC reporting requirements
AE	Sponsor	Recommended within 10 working days
	IRB/EC	Per IRB/EC reporting requirements
SAE	Sponsor	Recommended within 10 working days
	IRB/EC	Per IRB/EC reporting requirements
ADE	Sponsor	Recommended within 10 working days
	IRB/EC	Per IRB/EC reporting requirements
SADE	Sponsor	Recommended within 10 working days
	IRB/EC	Per IRB/EC reporting requirements

Table 6: Reporting Requirements Timeframe for Investigators

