12.4 Reporting of Adverse Events and Device Deficiencies

Investigators should assess and report the appropriate information on the AE eCRF for the following events, starting from the point of skin incision until the subject exits the study:

- o All AEs related to the MaxTack[™] Motorized Fixation Device, mesh, or study procedure
- o All events that lead to death, regardless of relatedness
- Any non-subject adverse event

Reporting requirements are noted in Section 12.3.1. Assessment of events will include date of event, relationship to study device, relationship to mesh, relationship to study procedure, description, seriousness, action(s) taken, date of resolution and outcome. Additionally, any medication/treatment administered to resolve an AE must also be reported.

Subject Status AE Reporting		AEs to Report Timeframe		
	Required			
Preoperative Screen failure	No	N/A		
Intraoperative Screen failure	No	N/A		
Enrolled	Yes	From skin incision through Study Exit (e.g., study completion, withdrawal or LTFU)		

 Table 7: Subject Status Adverse Event Reporting

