13.1 Independent Medical Monitor

At regular intervals, an independent Medical Monitor (MM) will conduct an independent adjudication of specified adverse events for subjects participating in the study. Source documents to support adjudication may be requested.

The MM will be a board-certified/board-eligible physician with expertise in hernia surgery and experience in the use of similar tacking devices. This physician will not be employed by Medtronic, will not be a participating investigator in the study, and will possess the necessary qualifications through education, training, and relevant experience to oversee the product's use and associated procedures.

Most adjudications will be conducted independently by the MM via entry of their assessments into the database. Medtronic personnel may facilitate adjudication meetings if needed, but the final adjudication decision will be solely from the MM.

If the MM disagrees with the investigator's classification of the event, the MM assessment will be provided to the investigator. If the investigator agrees with the MM's adjudication, the investigator is responsible for updating the AE CRF accordingly.

If the investigator does not agree with the MM's adjudication classification, both determinations will be provided within the final report; however, the MM's adjudication will be used for data analysis. If required, both determinations will be included in reporting to IRB/ECs and regulatory authorities.

14. Statistical Design and Methods

This section presents statistical considerations and justification for the study design and provides a highlevel description of planned analysis and reporting. More details will be given in a separate Statistical Analysis Plan (SAP) that will be finalized and approved before first data freeze or lock. Any deviation to the prespecified statistical analyses including justification, will be noted in the clinical study report(s).

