All participating sites will make study data available to the regulatory body if the regulatory body deems an onsite inspection necessary. The regulatory body will be able to inspect records at clinical study sites to resolve any uncertainties about whether the study was conducted in accordance with good clinical practice.

The study will be publicly registered prior to in accordance with the 2007 Food and Drug Administration Amendments ACT (FDAAA) and DoH on http://clinicaltrials.gov (PL 110-85, Section 810(a)).

Approval of the CIP and CIP amendments is required from the following groups prior to any study procedures / revised study procedures at a study site:

- Medtronic
- IRB/EC

This study contains the following from ISO 14155:2020:

AFFIX (MaxTac Clinical Investig				
MDT23014	Revision	3.0	Page 63 of 97	Medtronic

- Point of Enrollment: Per ISO 14155:2020, the point of enrollment is the time at which, following recruitment and before any clinical investigation-related procedures are undertaken, a subject signs and dates the informed consent form. In this study, a subject is considered enrolled when it is confirmed: the ICF is obtained, they meet all preoperative inclusion criteria, and they do not meet any preoperative or intraoperative exclusion criteria, and at least one MaxTack[™] tack is used. (See Section 10.6 for Enrollment details). Those subjects who sign the ICF but fail all screening criteria, will not be included in the study. Those subjects who sign the ICF and are considered intraoperative screen failures will not count as an enrollment.
- Adverse Event Collection: Per ISO 14155:2020, all AEs shall be documented. In this study, only AEs related to the MaxTack[™] motorized fixation device, mesh, or study procedure, all events that lead to death, and any non-subject adverse event will be collected. Additionally, adverse events will be collected starting at the time of skin incision. Enrolled subjects will have adverse events collected from skin incision through study exit.
- Unanticipated Serious Adverse Device Effect (USADE): Per ISO 14155:2020, USADEs are defined as, a SADE, which by its nature, incidence, severity, or outcome has not been identified in the current risk assessment. Due to this being a post-market study, USADEs are not applicable, therefore classification of AEs as such is not required.

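### The protocol gives independent review no route to correct a false not-related call on a nonfatal event, so SSO and SSOPI incidence may be under-counted

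*Protocol*

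**What the plan says.** Relatedness is part of the endpoint. Protocol Section 5.2.2 defines the first secondary endpoint as "Incidence of Surgical Site Occurrence (SSO) which are the following Adverse Events (AEs) related to the study device, mesh, and / or study procedure", limited to seroma, hematoma, surgical site infection and bleeding where a tack was placed. SSOPI is the subset needing a procedural intervention.

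Relatedness also decides what is entered. Section 12.4 says "Investigators should assess and report the appropriate information on the AE eCRF for the following events" and then lists events related to the device, mesh or procedure, fatal events and non-subject events. Section 12.1 has the same list, with one exception to the relatedness condition for subjects: "All events that lead to death, regardless of relatedness". Section 15.1 declares this as a departure from the standard: "Per ISO 14155:2020, all AEs shall be documented. In this study, only AEs related to the MaxTack" device, mesh or procedure, plus the fatal and non-subject events, are collected. Section 12.3.1 is worded more widely: "All AEs and DDs need to be reported in a timely manner to the sponsor".

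Review comes afterwards. Under Section 12.4.1 a sponsor representative reviews an event once it has been received, and the sponsor makes its own classification of relatedness and seriousness. Under Section 13.1 the independent Medical Monitor adjudicates specified adverse events, which that section does not list. If the Monitor and investigator still disagree, "both determinations will be provided within the final report; however, the MM's adjudication will be used for data analysis".

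The related group is broad. In Section 12.3 it "will include Possible, Probable and Causal", three of the four levels. Possible covers weak relationships with competing causes, and is also the default when relatedness cannot be assessed.

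**The concern.** Section 6 lists the Medical Monitor among the measures to control bias, and Section 6.1 describes SSOs as events of interest beyond recurrence. The relatedness call in this open, single-arm, sponsor-funded study is first made by an investigator, often the operating surgeon. An independent check on that call is useful only if it can correct errors in both directions. Here the judgement to be checked also decides whether the event is recorded. A nonfatal site event that an investigator positively attributes to something other than device, mesh and procedure does not have to be entered, so the Monitor has nothing to review. At stake is the credibility of the SSO and SSOPI rates as independently adjudicated figures.

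**Working it through.** **Step 1: the four cases.** Take a nonfatal seroma, hematoma, site infection or tack-site bleed in an enrolled subject.

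| Truth | Investigator's call | On the AE form? | Can the Monitor correct it? |
|---|---|---|---|
| Related | Related | Yes | Nothing to correct |
| Not related | Related | Yes | Yes, to not related |
| Related | Not related | Not required (12.1, 12.4, 15.1) | No route given |
| Not related | Not related | Not required | Nothing to correct |

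On relatedness, review can correct the second row but not the third. The third row contributes a downward error, or none if it is empty.

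**Step 2: what the size depends on.** Let p be the true incidence and q the share of true events that the investigator calls unrelated to all three of device, mesh and procedure. If the recorded events are left as they are,

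recorded rate = p × (1 − q), and loss = p × q.

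The protocol gives neither p nor q, and states no expected SSO rate or precision. So q is assumed at 2%, 5%, 10% and 20%. For p, two anchors come from Appendix I: procedure-related seroma in the sponsor's AbsorbaTack study, 12/54 = 22.2%, and seroma in its ReliaTack study, 3/40 = 7.5%. Both are rates of events that were attributed to the procedure. They only set a scale and are no evidence of under-attribution.

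| p | q = 0 | 2% | 5% | 10% | 20% |
|---|---|---|---|---|---|
| 22.2% | 22.2% | 21.8% | 21.1% | 20.0% | 17.8% |
| 7.5% | 7.5% | 7.35% | 7.1% | 6.75% | 6.0% |

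The loss runs from 7.5 × 0.02 = 0.15 points to 22.2 × 0.20 = 4.4 points, and is zero if q = 0.

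**Step 3: scale in this study.** With 110 subjects, p = 22.2% is 110 × 12/54 = 24.4 affected subjects, counting one event each. At q = 20%, 4.9 of them are missed. For comparison, the approximate 95% half-width is 1.96 × √(0.222 × 0.778 / 110) = 7.8 points. At p = 7.5% it is 1.96 × √(0.075 × 0.925 / 110) = 4.9 points, against a largest loss of 1.5 points. Even the largest assumed loss lies inside sampling error, but it would be systematic and the interval would not show it.

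**Step 4: the primary endpoint.** The stated design reproduces. With 100 evaluable subjects and a 1.0% rate, the chance of three or fewer recurrences is 98.2% (stated: over 90%). The Clopper-Pearson upper limit is 8.52% for 3/100, below 8.6%, and 9.93% for 4/100. Recurrence is assessed by examination at each follow-up visit (Sections 5.2.1 and 10.9), without a relatedness condition, so none of this moves.

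**The case against.** The strongest reply is that the third row may be nearly empty. An event counts if it is related to any one of device, mesh or procedure, and procedure-relatedness extends to anesthesia, incision, other fixation methods and skin closure. Possible expressly allows for an underlying illness or the effect of another drug. A hematoma in a patient on anticoagulants, or an infection in a diabetic patient, at the operated site would ordinarily fall there and be recorded. This stands as a limit on the size. It does not reach an event that the investigator positively calls unrelated, and Section 12.3 lists attribution to another cause among the grounds for that call.

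It is also fair that the restriction is declared in Section 15.1 for a cleared, post-market device, and that monitors check source records against the forms (Section 16.1.1). But leaving out an event judged unrelated complies with Sections 12.1 and 12.4, so a source check need not lead to its entry.

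A reader might infer more than the protocol supports:

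- **That review can never add an SSO or SSOPI.** The Monitor may disagree with the classification of an event, not only its relatedness. A recorded related event of another type could become an SSO, or an SSO an SSOPI. Sponsor queries may also bring out an unreported event.
- **That review can only lower serious adverse device effect counts.** Moving a recorded event from procedure-related to device-related, or from non-serious to serious, raises them.
- **That Table 6 contradicts Section 12.1.** Its AE and SAE rows are needed for events related only to the procedure and for unrelated deaths, neither of which is a device effect. The table sets timeframes and Section 12.4 sets the scope. The opening of Section 12.3.1 is at most loosely worded.
- **That every SAE should be collected.** A bowel admission, for example, is not an SSO component. Wider SAE collection is a separate trade-off within a declared scope.

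**Conclusion.** The point holds in a limited form. For nonfatal events in enrolled subjects, the protocol lets the Medical Monitor downgrade a related event but provides no route to correct a false not-related call. SSO and SSOPI incidence may therefore be under-counted. This is a possibility and not a demonstrated bias: the direction on this pathway is down or zero, and the size cannot be derived from the protocol. The 0.15 to 4.4 points shown rest on assumed values of q between 2% and 20% and on seroma rates borrowed from two earlier device studies. Section 14.8 makes all secondary endpoints descriptive, so no test or success criterion changes. This is a cheap improvement to the study's safety events of interest, not a threat to its main conclusion.

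**What to change.** In Sections 12.1, 12.4 and 15.1, require every seroma, hematoma, surgical site infection and tack-site bleeding event in an enrolled subject to be recorded whatever the investigator's relatedness call. In Section 13.1, name these four types among the specified events that the Medical Monitor adjudicates. The endpoint definitions can stay, because the Monitor's call on relatedness already governs the analysis and the rule for disagreement is already written. Keep the related-only rule for all other nonfatal subject events. In Section 12.3.1, replace the reference to all AEs by all reportable AEs per Section 12.1, and carry the wording into the synopsis.

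The cost is a protocol wording change, a few extra AE forms and a few extra Monitor reviews within an existing role. The reported SSO rate may come out slightly higher.

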16.1 Monitoring

It is the responsibility of Medtronic to ensure proper monitoring of this study. Authorized Medtronic representatives will perform study monitoring activities in accordance with Medtronic SOPs and the study Monitoring Plan, to ensure the study is conducted in accordance with this CIP, the CTA, and the applicable regulatory and local requirements. These Medtronic representatives must therefore be allowed direct access to subjects' medical and study records (clinic and hospital records, and other source data /

AFFIX (MaxTac Clinical Investig				
MDT23014	Revision	3.0	Page 64 of 97	Medtronic

documentation) upon request. The principal investigator should make every attempt to be available during monitoring visits.

16.1.1 Monitoring Visits

Monitoring for the study includes site initiation visits, interim monitoring visits, and closeout visits, and may be performed via in person visits or remotely, when applicable.

Site initiation visits will be completed prior to enrollment of the first subject to ensure appropriate site staff are trained and delegated where applicable, and all required study documents are completed and collected.

Frequency of interim monitoring visits may be based upon subject enrollment, study compliance, number of adverse events, number of deviations, observations from previous monitoring visits and any suspected inconsistency in data that requires investigation. Monitoring visits may be conducted periodically to assess study site progress, the investigator's adherence to the CIP, regulatory compliance, maintenance of records and reports, and review of source documents against subject CRFs in accordance with the study-specific monitoring plan. To ensure the rights, safety, and welfare of study subjects are being maintained, the monitor will maintain assurance that all study staff are trained on the CIP and use of the study devices.

Monitors review study site regulatory and study compliance by identifying observations of noncompliance and communicating those observations along with recommendations for preventative/corrective actions to study site personnel. Monitors may work with study personnel to determine appropriate corrective action recommendations and to identify trends within the study or at a particular study site. If the monitor discovers that an investigator is not complying with the signed Investigator Statement, the CIP, applicable laws, or any conditions of approval imposed by the reviewing IRB/EC, the monitor will report to the Sponsor and take such steps necessary to promptly secure compliance. If compliance cannot be secured, the investigator's participation in the investigation may be terminated.

A closeout visit will occur once a site has fulfilled (or mostly fulfilled) all requirements for the clinical study and/or the study is terminated. The visit will include a review of any outstanding items and final steps and/or obligations in the study.

16.2 Data Management

Data will be collected using an electronic data management system for studies. CRF data will be stored in a secure, password-protected database, backed up nightly. Data will be reviewed using programmed and manual data checks. Data queries will be made available to study sites for resolution. Study management reports may be generated to monitor data quality and study progress. At the end of the study, Medtronic will lock and retain the data per applicable regulations.

AFFIX (MaxTa Clinical Invest				
MDT23014	Revision	3.0	Page 65 of 97	Medtronic

All records and other information about subjects participating in this study will be treated as confidential. Data will be transferred and processed by Medtronic, or a third party designated by Medtronic, in a key coded form unless it's impossible to pseudonymize, for instance, where the subject's name cannot be removed from the data carrier, such as CT images.

Procedures in the CIP require source documentation. Source documentation will be maintained at the study site. The study site team must create and maintain source documents, which may include worksheets and subject medical records.

The investigator will clearly mark clinical records to indicate that the subject is enrolled in this clinical investigation.

The data reported on the eCRFs shall be derived from source documents and be consistent with these source documents, and any discrepancies shall be explained in writing. See Section 10.12 for CRFs and data collection elements that may be considered as source.

